#### **3.5.5.2 Statistical Methods for Safety Analyses**

All subjects who received at least 1 dose of GARDASIL®9 and have safety follow-up data will be included in the analysis of safety.

Prevalence of safety measures will be described with 95% CI and will be compared to the prevalence in historical controls with a test for proportions. Regardless of incidence, all AEs will be summarized as frequencies and percentages by vaccination visit, and across all vaccination visits. Specific AEs for which summaries will be provided are identified in Table 6. Incidence is defined as (number of subjects

with the indicated endpoint divided by the total number of subjects with follow-up over the relevant period) × 100%. Confidence intervals (95%) and 2-sided p-values will be provided without adjusting for multiplicity. Treatment administration data will be summarized for including number of vaccine injections received. Imputation methods will not be used to replace missing safety data. Safety data for HIV patients and SOT patients will be analysed separately.

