### 2.2.2. Secondary Objective(s):

#### SAFETY

To determine the *safety and tolerability* of Gardasil®9 with respect to HPV types 6, 11, 16, 18, 31, 33, 45, 52 and 58 in adult HIV (age: 18-46 years) and solid organ transplant patients (age: 18-55 years).

**Hypothesis:** GARDASIL®9 is well tolerated 18-45-year-old **HIV patients** compared to healthy subjects as evaluated by the occurrence of local and systemic reactions following vaccination.

**Hypothesis:** GARDASIL®9 is well tolerated by 18-55-year-old **solid organ transplant patients** compared to healthy subjects as evaluated by the occurrence of local and systemic reactions following vaccination.

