### **2.5.2 Treatment plan**

All enrolled 100 HIV patients and 170 SOT patients will receive GARDASIL®9 as a 3-dose regimen of 0.5-mL intramuscular injections administered on Day 1, Month 2, and Month 6. Study vaccine must be stored in a refrigerator that has a temperature between 2 °C and 8°C. If the refrigerator in which the study vaccine is stored deviates from the 2°C to 8°C range, study vaccinations should be suspended and MSD should be contacted immediately so that an investigation can be conducted.

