**Table 6: Analysis Strategy for Safety Parameters**

Adverse Event Endpoint	Follow-Up Period		Summaries/Analyses			
	After Any Vaccination Visit		Any Time During Study	Incidence	Risk Difference and 95% CI (b)	p-Value
	Day 1 to Day 5 (a)	Day 1 to Day 15 (a)				
Clinical AE						

 
Any AE
 
Death
 
		•	•	•		

 
Injection-site adverse events (c)
 
						

 
Injection-site pain/tenderness, swelling, and redness
 
Other injection-site adverse reactions
 
Severe injection-site adverse reactions
 
Number (%) of subjects by maximum intensity rating, over all injection-site adverse reactions
 
Number (%) of subjects by maximum intensity rating, within each of the categories of injection-site adverse reactions
 
	•			•	• (d)	•
Systemic AEs						

 
Systemic AEs
 
Number (%) of subjects by maximum intensity rating, over all systemic AEs
 
		•		•	• (e)	
Temperatures						

 
Elevated temperatures (f)
 
Maximum temperatures (g)
 
	•			•	•	•

AEs of special interest						

 
• Serious AEs
 
• Serious VR AEs
 
• New medical conditions
 
		•	•	•	•	

(a) The day of vaccination is counted as Day 1.
 
(b) Defined as the difference in incidence between the comparison groups (SOT and HIV patients versus historical controls).
 
(c) For the injection-site redness and swelling 0 to 2.5 cm (0 to 1 inch) will be categorized as mild, >2.5 to 5 cm (>1 inch to 2 inches) will be categorized as moderate, and >5 cm (>2 inches) will be categorized as severe.
 
(d) Only for injection-site adverse reactions occurring in <math>\geq 1\%</math> of subjects in either group.
 
(e) Only for systemic AEs occurring in <math>\geq 1\%</math> of subjects in either group.
 
(f) Defined as maximum (over the follow-up period) temperature <math>\geq 37.8^\circ\text{C}</math>.
 
(g) Distribution of maximum temperatures over the relevant follow-up period.
 
AEs, adverse events; VR, vaccine-related.
						

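### The tolerability hypotheses are no-worse claims, but the planned tests are two-sided difference tests, and no limit links the planned risk-difference interval to the conclusion

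*Combined protocol and SAP*

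**What the plan says.** Section 2.2.2 (Safety) states one hypothesis per cohort: the vaccine is well tolerated "compared to healthy subjects as evaluated by the occurrence of local and systemic reactions following vaccination". It gives no numerical criterion.

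Section 3.5.5.2 gives the method: the prevalence of each safety measure gets a 95% interval and "will be compared to the prevalence in historical controls with a test for proportions". It adds: "Confidence intervals (95%) and 2-sided p-values will be provided without adjusting for multiplicity". The cohorts are not pooled: "Safety data for HIV patients and SOT patients will be analysed separately".

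Table 6 asks for a risk difference with a 95% interval, which note (b) explains as "Defined as the difference in incidence between the comparison groups (SOT and HIV patients versus historical controls". As the table can be read, the injection-site block (which includes "Severe injection-site adverse reactions") and the temperature block carry incidence, risk difference and p-value. The systemic adverse event block carries incidence and risk difference, with no p-value mark.

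Sections 1.4 and 2.5.1 say that enrolment numbers were set by the primary immunogenicity objective. Section 3.5.6 gives precision and power for immunogenicity only.

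**The concern.** Well tolerated compared with healthy people is a one-directional claim: reactions are not unacceptably more frequent. A test of equal proportions can show that rates differ, but cannot show that an excess is small. If the test is set against the hypothesis, the outcome that leaves the hypothesis standing is a non-significant one, and that becomes easier to obtain as the evaluable sample shrinks. A significantly lower reaction rate would register as a difference although it does not contradict tolerability.

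At stake is what the report may say about infrequent but important reactions, such as severe local reactions and fever. With 100 and 170 patients and no stated limit, a tolerability statement could rest on data that do not exclude a material excess.

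**Working it through.** **Inputs from the documents.** Section 2.5.2: "All enrolled 100 HIV patients and 170 SOT patients will receive GARDASIL®9". Two-sided p-values and 95% intervals come from section 3.5.5.2; a 5% level is implied by the intervals but not stated. Control incidences and control sample sizes are not given, so both are assumptions below.

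**The plan's own figures.** Section 3.5.6 uses the half-width 1.96 × √(p(1−p)/n):
- SOT, 80%, n=170: 1.96 × √(0.8 × 0.2/170) = 6.0 points (stated ±6%).
- HIV, 90%, n=80: 1.96 × √(0.9 × 0.1/80) = 6.6 points (stated ±6.6%).
- HIV, 95% and 99%, n=80: 4.8 and 2.2 points (stated ±4.8% and ±2.2%).

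These reproduce. They concern seroconversion; there is no corresponding safety figure.

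**Chance that a true doubling is non-significant.** Exact two-sided one-sample binomial test at 5% against a fixed control rate p0. For each n, find the counts x with p > 0.05, then sum the Binomial(n, 2·p0) probabilities over them. Example, p0 = 5%, n=100: counts 1 to 9 are non-significant (p = 0.10 at 9, p = 0.034 at 10), and P(1 ≤ X ≤ 9 | 10%) = 45%.

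| Control rate → true rate | HIV n=100 | SOT n=170 |
|---|---|---|
| 2% → 4% | 79% | 63% |
| 3% → 6% | 61% | 43% |
| 5% → 10% | 45% | 27% |
| 8% → 16% | 25% | 8% |
| 10% → 20% | 19% | 5% |

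For a common reaction, a rise from 40% to 50% is missed in 54% (HIV) and 30% (SOT).

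**Finite control sample.** Two-sample calculation for a doubling from 3% and from 5%:
- 1000 controls: HIV 61% and 46%; SOT 49% and 31%.
- 250 controls: HIV 71% and 58%; SOT 67% and 50%.

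Most cases are worse than with a fixed rate, though not all: at 2% with 1000 controls the figures are 69% (HIV) and 61% (SOT).

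**What one non-significant result can hide.** With a 5% control rate, 9 reactions in 100 HIV patients gives p = 0.10. The exact 95% upper limit is 16.4%, more than three times the control rate.

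**What an interval criterion could show.** As an illustration only, take the limit to be a doubling of a fixed control rate, and let the true rate equal control. The probability that the exact 95% upper limit falls below 2·p0 is:
- p0 = 3%: HIV 20%, SOT 42%.
- p0 = 5%: HIV 44% (needs at most 4 of 100), SOT 66% (at most 9 of 170).
- p0 = 10%: HIV 70%, SOT 95%.

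**The case against.** The strongest reply is that the plan does not depend on tests alone. It describes every prevalence with a 95% interval, and Table 6 requires risk differences with intervals. For systemic adverse events it appears to plan estimation without a p-value. Safety is secondary, its p-values are openly unadjusted, and the sample size was openly set on immunogenicity. This stands in part: the excess that the data cannot rule out can be read from the planned output. What is missing is anything to judge it against, or a statement that the interval rather than the p-value carries the conclusion.

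A reader might infer that the plan treats p > 0.05 as proof of tolerability. No section says so. The gap is that no rule is given at all, for hypotheses that are formally stated.

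A reader might also infer that the plan misses a doubling of severe reactions or fever in about a quarter to over half of trials. The documents do not support that as a property of the plan. It fits assumed control rates of about 3% to 5% only. In the SOT cohort, with a fixed control rate, a doubling from 6% is missed in 18% and from 8% in 8%.

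The complaint about two-sidedness is minor, since the sign of the risk difference shows a lower rate for what it is. The seroconversion hypothesis has a related weakness, but this point concerns a one-directional harm question on other endpoints.

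**Conclusion.** The point holds at any control rate: a no-worse hypothesis is paired with two-sided difference tests, and nothing ties the conclusion to the risk-difference interval already planned. A non-significant result would not support section 2.2.2.

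The size depends on control rates that the documents do not give. With a fixed control rate between 2% and 10%, a true doubling goes undetected in 79% down to 19% of trials for HIV and 63% down to 5% for SOT. A finite control sample raises most of these figures. The calculation assumes a 5% level and all 100 and 170 patients evaluable. Because safety is secondary and the intervals will be reported, this should be corrected but does not threaten the primary analysis.

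**What to change.** In section 3.5.5.2 and Table 6, state that:
- the tolerability conclusion for injection-site reactions, systemic adverse events and elevated temperature rests on the upper limit of the 95% interval for the risk difference (patients minus controls), with control sampling error included;
- p > 0.05 is not evidence of tolerability, and a lower rate does not contradict it;
- the report gives, for each endpoint, the excess that the data cannot rule out.

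If a formal tolerability conclusion is kept, the clinical team should fix the largest acceptable excess per endpoint, and say whether all endpoints must meet it, before any reactogenicity data are summarised. The study is open-label, diaries are reviewed from Visit 2 (section 3.1.10), and the rationale for Amendment 1 reports 69 HIV patients already enrolled. If patients are already enrolled, the sponsor should therefore document that the limits were set without reference to their data. Otherwise, reword the section 2.2.2 hypotheses as estimation objectives and drop the p-values.

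The cost is protocol and SAP wording, with no added patients or data. The real downside is that infrequent reactions may not support a firm statement, especially in the HIV cohort. At an observed 5%, the half-width 1.96 × √(0.05 × 0.95/n) is 4.3 points for HIV and 3.3 for SOT, before control sampling error. The illustrative power of 44% and 66% at a 5% control rate shows the same limit.

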**Table 6: Analysis Strategy for Safety Parameters**

Adverse Event Endpoint	Follow-Up Period		Summaries/Analyses			
	After Any Vaccination Visit		Any Time During Study	Incidence	Risk Difference and 95% CI (b)	p-Value
	Day 1 to Day 5 (a)	Day 1 to Day 15 (a)				
Clinical AE						

 
Any AE
 
Death
 
		•	•	•		

 
Injection-site adverse events (c)
 
						

 
Injection-site pain/tenderness, swelling, and redness
 
Other injection-site adverse reactions
 
Severe injection-site adverse reactions
 
Number (%) of subjects by maximum intensity rating, over all injection-site adverse reactions
 
Number (%) of subjects by maximum intensity rating, within each of the categories of injection-site adverse reactions
 
	•			•	• (d)	•
Systemic AEs						

 
Systemic AEs
 
Number (%) of subjects by maximum intensity rating, over all systemic AEs
 
		•		•	• (e)	
Temperatures						

 
Elevated temperatures (f)
 
Maximum temperatures (g)
 
	•			•	•	•

AEs of special interest						

 
• Serious AEs
 
• Serious VR AEs
 
• New medical conditions
 
		•	•	•	•	

(a) The day of vaccination is counted as Day 1.
 
(b) Defined as the difference in incidence between the comparison groups (SOT and HIV patients versus historical controls).
 
(c) For the injection-site redness and swelling 0 to 2.5 cm (0 to 1 inch) will be categorized as mild, >2.5 to 5 cm (>1 inch to 2 inches) will be categorized as moderate, and >5 cm (>2 inches) will be categorized as severe.
 
(d) Only for injection-site adverse reactions occurring in <math>\geq 1\%</math> of subjects in either group.
 
(e) Only for systemic AEs occurring in <math>\geq 1\%</math> of subjects in either group.
 
(f) Defined as maximum (over the follow-up period) temperature <math>\geq 37.8^\circ\text{C}</math>.
 
(g) Distribution of maximum temperatures over the relevant follow-up period.
 
AEs, adverse events; VR, vaccine-related.
						

### 3.5.5.3 Summaries of Baseline Characteristics, Demographics, and Other Analyses

Baseline characteristics and demographic variables will be summarized for HIV and SOT patients using descriptive statistics or categorical tables on all subjects enrolled in the study and on all PPI eligible subjects (i.e., subjects belonging to at least one PPI analysis populations). No formal statistical testing of differences with census data from patient populations with respect to these characteristics will be performed.

Quantitative variables (except antibody titres) will be displayed using descriptive statistics by way of sample size, mean, standard deviation, median, minimum, and maximum. Antibody titres will be displayed using descriptive statistics by way of sample size, GMT s, and two-sided 95% CIs.

Categorical variables will be displayed using descriptive statistics by way of sample size, count by category, and proportion by category. Missing data will be counted but not included in the calculation of proportions.

#### Subject Accounting

The number and percentage of subjects screened (ICF signed), enrolled (allocation number assigned), vaccinated (at least once and at each vaccination time point), discontinued, and the primary reason for discontinuation will be displayed for HIV and SOT patients. Reasons for subjects excluded from the PPI analysis populations will be summarized and displayed in subject accounting tables.

### Subject Characteristics

Demographic variables and other baseline characteristics such as age, vital signs (height, weight, and oral temperature), and country of origin will be summarized for both HIV and SOT patients.

### Baseline HPV Status

A serum sample will be collected from all subjects at the Day 1 visit for the purpose of assessing baseline HPV serostatus to the 9vHPV vaccine HPV types (HPV 6, 11, 16, 18, 31, 33, 45, 52, and 58). A subject will be considered seropositive to a given HPV type at Day 1 if the subject's anti-HPV titre is greater than or equal to the corresponding serostatus cutoff for that HPV type or seronegative to a given HPV type at Day 1 if the subject's anti-HPV titre is less than the corresponding serostatus cutoff for that HPV type. For each HPV type, the proportions of subjects who are seronegative or seropositive will be summarized for both HIV and SOT patients.

### Prior and Concomitant Medications

The number and percentage of subjects with prior medications or vaccinations prior to each study vaccination will be summarized for both HIV and SOT patients. The relevant pre-injection day ranges for summarization will be 3 days for medications, 14 days for non-live virus vaccines, and 28 days for live virus vaccines.

Similarly, the number and percentage of subjects with concomitant medications or vaccinations within 15 days (Day 1 to Day 15) following any study vaccination will be summarized for each age group. The number of subjects with "Special Medications" (corticosteroids, immunosuppressives, immune globulins, and blood products [Section 3.2.4]) will be summarized for both HIV and SOT patients throughout the study period.

New Medical Conditions: New medical conditions occurring during the study (i.e., incident medical conditions occurring outside of a Day 1 to Day 15 period post -vaccination and not considered SAEs) will be summarized for both HIV and SOT patients.

### **3.5.6 Sample Size and Power Calculations**

Based on an expected seroconversion rate of 80%, a sample size of 170 transplant patients allows to estimate the proportion of protected transplant patients with precision (95% confidence interval) of  $\pm 6\%$  (10).

Furthermore, based on an expected seroconversion rate 85-91%, a sample size of 140 HIV-patients allows to estimate the proportion of protected patients with precision (95% confidence interval) of  $\pm 6\%$  and 5% respectively (7). Based on expected differences in GMT to healthy populations, a sample size of 140 HIV-patients allows to estimate the GMTs HPV type 6, 11, 16 and 18 with a power of 0.38, 0.82, 1 and 1, respectively (7, 19).

Due to difficulties in the recruitment of HIV patients without genital warts a recalculation of the sample size was done. With a total sample size of  $n=100$ , a majority of whom will have no history of HPV-lesions, we expect to be able to use the data of at least 80 patients for the analysis seroconversion of each HPV type under study. Seroconversion rates of 95-99% for HPV types 6, 11 and 16 can then be

estimated with a margin of error of  $\pm 4.8\%$  -  $2.2\%$ , and the anticipated seroconversion rate of 90% for HPV type 18 with a margin of error of  $\pm 6.6\%$ .

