- The expected seroconversion rates that were used for the sample size calculation were retrieved from published data of patients with a CD4-count of 200-350 cells/mm^2. However, 92% of the patients that are currently included have a CD4-count of  $> 350$  cells/mm^2, which makes seroconversion rates in patients with more than 350 CD4+ cells/mm^2 more applicable (1). Published seroconversion rates in these patients are 95%-99% for HPV types 6, 11 and 16 and 90% for HPV-18.
- This sample size calculation does not take in to account that patients might be seropositive to certain HPV-types at baseline and that their data will be excluded for the analysis of the seroconversion outcome of the corresponding HPV-type. Seroprevalence to different HPV-types in previous studies on the safety and immunogenicity of the quadrivalent HPV-vaccine in HIV patients ranged from 13% to 45% for the different vaccine HPV-types (1-3).
- In order to maximize the number of eligible subjects, we amend the protocol to also **include patients with a history of abnormal PAP-smears without treatment or genital warts**. We believe that this allows us to reach a total sample size of at least 100 HIV-patients. Patients who are seropositive for a given HPV-type at baseline will

still be excluded for the analysis of seroconversion of that particular type but will still be useful for the analysis of the other HPV-types. Knowing that in HIV-patients the expected seroconversion rate of HPV-18 is relatively lower than the seroconversion rates of HPV types 6, 11 and 16, maximizing the number of eligible subjects for the analysis of this type is especially beneficial in order to obtain a reasonable margin of error. Enrolling patients with history of genital warts, who are most likely seropositive to HPV types 6 or 11, still allows us to increase the number of HPV-18 seronegative patients. In addition, clinical presentation of HPV infection does not necessarily implicate seropositivity to HPV.

- **With a total sample size of n=100, a majority of whom will have no history of HPV-lesions, we expect to be able to use the data of at least 80 patients for the analysis seroconversion of each HPV type under study. Seroconversion rates of 95-99% for HPV types 6, 11 and 16 can then be estimated with a margin of error of  $\pm 4.8\%$  -  $2.2\%$ , and the anticipated seroconversion rate of 90% for HPV type 18 with a margin of error of  $\pm 6.6\%$ .**

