**The amendment to the study protocol therefore includes an adaptation of the study protocol which consists of a reduction of the planned sample size (from 140 to 100), and a wider recruitment in order to fulfil the aims of the study.**

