#### 1.4. Summary of study design

This is a single-center, open-label study on safety, tolerability and immunogenicity of Gardasil® in 18 to 45 year-old HIV patients, in 18 to 55 year-old solid-organ transplant (SOT) patients.

This study will enrol 100 HIV patients with CD4+ count of >200cells/mm^2 and 170 SOT patients, all of whom have not yet received a prophylactic HPV vaccine. The 170 SOT patients will be equally divided over 3 different SOT patient groups, namely heart, lung and kidney transplant patients. Therefore the target is to include approximately 57 heart transplant patients, 57 lung transplant patients and 57 kidney transplant patients. Enrolment in a SOT subgroup will be stopped when 57 patients have been included unless recruitment cannot be achieved within one of the other SOT-patient population.

All enrolled subjects will receive a 3-dose regimen (Day 1, Month 2, and Month 6) of GARDASIL®. Serum samples will be collected on Day 1 and Month 7 for anti-HPV 6, 11, 16, 18, 31, 33, 45, 52, and 58 antibody determination. The time point for comparison of immune responses will be Month 7, or approximately 4 weeks after the administration of the third dose. The safety/tolerability profile of the vaccine will be evaluated in all subjects in the study. Safety information will be collected on Day 1 through 1 month following the third vaccination or for a total of approximately 7 months for each subject.

The immunogenicity and the safety data will be analyzed per group of patients. More specifically a separate analysis of HIV and SOT patients is planned, since it is expected that the immunosuppressive therapy of SOT patients might have a more profound effect on immunogenicity following vaccination.

This study will provide a comparison of immunogenicity of Gardasil® in immunocompromised patients, with historical controls (15, 18). The number of subjects to be enrolled in the study was determined based on the primary immunogenicity objective.

---

 GARDASIL® (Human Papillomavirus 9-valent Vaccine, Recombinant) is a registered trademark of Merck Sharp & Dohme Corp., a subsidiary of Merck & Co., Inc., Whitehouse Station, New Jersey, U.S.A

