## **2.5. Study design and duration**

### **2.5.1. Study design summary**

This is a single-center, open-label study on immunogenicity and tolerability of Gardasil®9 in 18 to 45 year-old HIV patients, in 18 to 55 year-old solid-organ transplant (SOT) patients.

This study will enrol 100 HIV patients with CD4+ count of >200cells/mm^2 and 170 SOT patients, all of whom have not yet received a prophylactic HPV vaccine. The 170 SOT patients will be equally divided over 3 different SOT patient groups, namely heart, lung and kidney transplant patients. Therefore the target is to include approximately 57 heart transplant patients, 57 lung transplant patients and 57 kidney transplant patients. Enrolment in a SOT subgroup will be stopped when 57 patients have been included unless recruitment cannot be achieved within one patient population.

All enrolled subjects will receive a 3-dose regimen (Day 1, Month 2, and Month 6) of GARDASIL®9. Serum samples will be collected on Day 1 and Month 7 for anti-HPV 6, 11, 16, 18, 31, 33, 45, 52, and 58 antibody determination. The time point for comparison of immune responses will be Month 7, or approximately 4 weeks after the administration of the third dose. The safety/tolerability profile of the vaccine will be evaluated in all subjects in the study. Safety information will be collected on Day 1 through 1 month following the third vaccination or for a total of approximately 7 months for each subject.

The immunogenicity and the safety data will be analyzed per group of patients. More specifically a separate analysis of HIV and SOT patients is planned, since it is expected that the immunosuppressive therapy of SOT patients might have a more profound effect on immunogenicity following vaccination.

This study will provide a comparison of immunogenicity of Gardasil ®9 in immunocompromised patients, with historical controls (15, 18). The number of subjects to be enrolled in the study was determined based on the primary immunogenicity objective.

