#### **3.5.3 Analysis Endpoints**

##### **3.5.3.1 Immunogenicity**

The immunogenicity endpoints are:

- The cLIA GMTs to HPV 6, 11, 16, 18, 31, 33, 45, 52 and 58 at 4 weeks after Dose 3.
- The cLIA seroconversion percentages to HPV 6, 11, 16, 18, 31, 33, 45, 52 and 58 by 4 weeks after Dose 3.

A subject with a cLIA titre at or above the serostatus cutoff for a given HPV type (see Section 3.3) is considered seropositive for that type. Seroconversion is defined as changing serostatus from seronegative at Day 1 to seropositive, by 4 weeks after Dose 3.

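### The GMT power in section 3.5.6 is still given only for 140 HIV patients, although Amendment 1 cut enrolment to 100 and updated only the seroconversion margins

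*Combined protocol and SAP*

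**What the plan says.** Section 3.5.6 gives two results for 140 HIV patients. The first is a seroconversion precision of about 6 and 5 points for rates of 85% and 91%. The second is GMT power: "a sample size of 140 HIV-patients allows to estimate the GMTs HPV type 6, 11, 16 and 18 with a power of 0.38, 0.82", with 1 and 1 for HPV 16 and 18. The power is said to rest on expected GMT differences from healthy populations, with two literature citations. The differences, log-titre SD, alpha, sidedness and test are not given.

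The next paragraph reports a recalculation for a total of 100, in which "we expect to be able to use the data of at least 80 patients for the analysis seroconversion of each HPV type under study". It gives seroconversion margins of 4.8 to 2.2 points for HPV 6, 11 and 16 and 6.6 points for HPV 18. It does not mention GMT. The Rationale for Amendment 1 likewise reworks only seroconversion.

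The current target is stated elsewhere in the body: "This study will enrol 100 HIV patients with CD4+ count of" more than 200 (section 2.5.1), and "All enrolled 100 HIV patients and 170 SOT patients will receive" the vaccine (section 2.5.2).

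GMT is still analysed. Section 3.5.3.1 lists "The cLIA GMTs to HPV 6, 11, 16, 18, 31, 33, 45, 52 and 58 at 4 weeks after Dose 3" as an immunogenicity endpoint, and section 3.5.5.1 plans a one-sample t-test of Month 7 GMTs against historical controls. The same section names seroconversion as the primary outcome. Section 1.4 says of the sizing: "The number of subjects to be enrolled in the study was determined based on the primary immunogenicity objective".

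**The concern.** The n=140 calculation had two parts, and only one of them has a successor. The only power figures in the plan belong to a sample size that is no longer planned, for a comparison that is still to be made.

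What is at stake is interpretation. If the HPV 11 GMT difference from controls turns out non-significant, someone relying on section 3.5.6 could treat it as the result of a test with 82% power, when the current design would give less if the original effect holds. HPV 6 was already low at 0.38. HPV 16 and 18 were printed as 1 and have more room to fall.

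**Working it through.** **Inputs from the documents.** n=140 and powers 0.38, 0.82, 1, 1 (section 3.5.6); 100 enrolled (sections 1.4, 2.5.1, 2.5.2); at least 80 usable per type (section 3.5.6); baseline seroprevalence 13% to 45% by type (Rationale for Amendment 1); one-sample t-test (section 3.5.5.1).

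**Assumed, because not stated.** Two-sided alpha 0.05; the planned one-sample t-test was also the test behind the powers; the original standardised effect d is unchanged.

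**Step 1: the plan's own figures.** Margin = 1.96 × √(p(1−p)/n).
- n=140: 85% gives 5.91 points, 91% gives 4.74.
- n=80: 95% gives 4.78, 99% gives 2.18, 90% gives 6.57.

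All reproduce, so the seroconversion half was updated correctly. The GMT powers cannot be reproduced, because their inputs are missing.

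**Step 2: back-solve d from the stated power.** Power = P(|T| > t(0.975, n−1)), where T is noncentral t with n−1 df and noncentrality d√n. At n=140:
- 0.38 gives d = 0.1408.
- 0.82 gives d = 0.2447 (noncentrality 0.2447 × √140 = 2.895, critical value 1.977).
- A printed 1 cannot be inverted. If it means at least 0.995, d is at least 0.386.

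**Step 3: hold d and change n.** For HPV 11 the noncentrality is 2.447 at n=100 and 2.189 at n=80.

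| n | Basis | HPV 6 | HPV 11 | HPV 16, 18 (if printed 1 is ≥0.995) |
|---|---|---|---|---|
| 140 | enrolled, before the amendment | 0.38 | 0.82 | ≥0.995 |
| 100 | enrolled, now | 0.29 | 0.68 | ≥0.97 |
| 112 | 80% of 140 usable | 0.32 | 0.73 | ≥0.98 |
| 80 | 80% of 100 usable | 0.24 | 0.58 | ≥0.93 |
| 87 | 100 less 13% seropositive | 0.26 | 0.62 | ≥0.94 |
| 55 | 100 less 45% seropositive | 0.18 | 0.43 | ≥0.80 |

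The Rationale says the original seroconversion sizing ignored baseline seropositivity, so its 140 was an enrolled count; the GMT power uses the same 140. The like-for-like comparisons for HPV 11 are therefore 0.82 to 0.68 (enrolled) or 0.73 to 0.58 (evaluable, 112 to 80). Going from 0.82 to 0.58 mixes the two bases.

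**Step 4: sensitivity, HPV 11.**
- One-sided 5%: 0.70 at n=100, 0.61 at n=80. Two-sided 1%: 0.64 and 0.52.
- Two-sample test with 140 to 3000 controls, two-sided 5%: 0.75 to 0.69 at n=100, 0.69 to 0.59 at n=80.
- d 20% smaller to 20% larger: 0.49 to 0.83 at n=100, 0.41 to 0.74 at n=80.
- Holding 0.82 needs d = 0.2904 at n=100 (0.2904/0.2447, about 19% larger) or 0.3254 at n=80 (about 33% larger).

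**The case against.** The best defence is that no one is misled and little depends on the figure. The sentence names 140 patients, and the next paragraph announces a recalculation for 100, so the n=140 text can be read as history. GMT has no stated hypothesis: both primary hypotheses in section 2.2.1 concern seroconversion, which also set the sample size. The plan accepted 0.38 for HPV 6 from the start, so adequate GMT power for every type was never a requirement. The illustrative powers also rest on inputs nobody outside the sponsor can see, and the effect itself may have moved. The Rationale says the reference data from patients with CD4 counts of 200 to 350 are less applicable because "92% of the patients that are currently included have a CD4-count of" more than 350.

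Most of this stands, and it limits the point to a correction of the text. It does not remove it. The sentences are in the current statistical section, half of that calculation was replaced and half was not, and the comparison is still planned. Doubt about the effect is a further reason to restate the power.

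Stronger readings are tempting but not supported:
- A reader might infer that the n=140 powers were miscalculated. The documents give no inputs with which to test that.
- A reader might infer that Amendment 1 alone took HPV 11 from 0.82 to 0.58. With 80% usable, 140 enrolled would already have given about 0.73.
- A reader might treat 80 evaluable as a floor, and so put the Day 1 seropositive set at no more than 20 per type. The plan's own 13% to 45% seroprevalence allows about 55 to 87 seronegative per 100 enrolled, before other exclusions.

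**Conclusion.** The point holds as an omitted update. Section 3.5.6 gives GMT power for 140 HIV patients only, the design is now 100, and no successor figure appears in the documents. That much can be read directly from the text.

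The size is indicative and conditional on 5% two-sided testing by one-sample t-test with the original effect. On the enrolled basis HPV 11 drops from 0.82 to about 0.68 and HPV 6 from 0.38 to about 0.29. On the evaluable basis HPV 11 is about 0.58 at 80, and about 0.43 to 0.62 over 55 to 87. A standardised difference about 19% larger than the original would restore 0.82 at n=100, so even the shortfall for HPV 11 is not certain.

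A reader might go further and conclude that the trial is underpowered for its main aim. The documents do not support that: seroconversion is the primary outcome, and its margins were restated and reproduce. The correction is worth making, but it changes no primary analysis.

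**What to change.** In section 3.5.6:
- Mark the n=140 GMT power as superseded by Amendment 1.
- Restate the power for HPV 6, 11, 16 and 18 from the sponsor's own inputs on two separate bases: 100 enrolled, and the expected evaluable number per type (at least 80 on the plan's expectation, with a sensitivity down to about 55).
- State the GMT differences, log-titre SD, alpha, sidedness and test, and whether the differences are the original ones or were revised for patients with CD4 counts above 350.
- Name the analysis population. Section 3.5.5.1 places the primary immunogenicity analyses in the per-protocol set (Day 1 seronegative for the type), while section 3.5.4.1 attaches the GMT label to the Day 1 seropositive set.

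The cost is a short recalculation and a few sentences, and the stated power will probably look less favourable. It needs no extra patients and no change to the primary outcome.
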